### 8.4 Study Drug Administration

RSLV-132 or placebo will be administered intravenously at 10 mg/kg at baseline, then weekly for two weeks and then once every 2 weeks for the next 20 weeks (13 administrations) to subjects with SLE. The preparation of the study drug and rate of infusion will be provided in the Study Drug Reference Manual. For each dose, the date, actual infusion rate, start and stop time of infusion will be recorded in the source documents and transcribed into the CRFs.

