2.3.5. Subject Withdrawal

Subjects will be informed that they are free to withdraw from the study at any time and for any reason. The Investigator may remove a subject from investigational treatment if, in the Investigator's opinion, it is not in the best interest of the subject to continue. Notification of discontinuation of investigational treatment will be made immediately to the Sponsor. In case of premature discontinuation of investigational treatment, efforts will be made to perform all End of Treatment (EOT) assessments and an End of Study (EOS) visit outlined in SAP Section 2.3.3 Table 1.

If a subject wishes to withdraw from the study, the site staff should confirm whether the subject is agreeable to continue the assessments without the investigational treatment or if they wish no further involvement in the study. In the latter case no further study-related evaluations will be performed and no additional data will be collected.

The date and the reason for discontinuation of investigational treatment or withdrawal from the study will be recorded on the subject's Case Report Form (CRF). Subjects that withdraw after receiving study drug will not be replaced.

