3.1.3. Safety Analysis Set

The Safety Analysis Set (SAS) is defined as all subjects who received any treatment with either RSLV-132 or placebo.

Randomized subjects that receive the incorrect therapy from that intended will be summarized in the group according to the therapy actually received. Subjects who are not randomized but who receive treatment or placebo will also be included and summarized according to the therapy actually received. In the unlikely event of a subject commencing one study therapy and crossing over to the other, the data for that subject will be included in summaries and analyses with the original group.

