6. SUBJECT DISPOSITION

6.1. Enrollment and Disposition of Subjects

Subjects' enrollment and disposition will be summarized by treatment group on two different analysis sets. The reasons for discontinuation will be listed in the order as they appear on the electronic case report form (eCRF).

Summary based on the ITT analysis set will include all randomized subjects and will be summarize for the following. The percentages will be calculated based on the number of subjects randomized in each of the treatment group.

- Number and percentage of subjects randomized
- Number and percentage of subjects randomized and discontinued prior to treatment
- The reason for discontinuation prior to treatment

Summary based on the FAS will include all randomized and treated subjects and will be summarize for the following. The percentages will be calculated based on the number of subjects randomized and treated in each of the treatment group.

- Number and percentage of subjects randomized and treated (Placebo or RSLV-132 10 mg/kg)
- Number and percentage of subjects randomized and treated who completed the study
- Number and percentage of subjects randomized and treated who discontinued from the study
- The reasons for study discontinuation
- Number and percentage of randomized and treated subjects included in each analysis set

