6.2. Extent of Exposure

RSLV-132 or Placebo will be administered intravenously at 10 mg/kg at baseline, then weekly for two weeks and then once every 2 weeks for the next 20 weeks (13 administrations) to subjects with SLE.

Total duration of study drug dosing (Days), total number of infusions, total duration of infusion (Hours), total volume infused (mL) and total duration of study drug exposure will be summarized by treatment group on SAS. The number and percentage subjects with overall

infusion status (completed, interrupted or terminated) during the treatment period and the reason for interrupted or terminated will be summarized by treatment group on SAS. The percentages will be calculated based on the number of subjects in each treatment group of the SAS.

Total duration of study drug dosing will be calculated as the total number of days from the first dose date to the last dose date plus 1 regardless of temporarily dose interruptions. Total number of infusions will be calculated as the sum from each infusion segment (if the infusion was interrupted and then started again). Total duration of infusion in hours will be calculated as the total minutes from each infusion segment (if the infusion was interrupted and then started again) start time to end time.

Overall infusion completed is defined as a subject without any infusion interruptions or terminations during the study.

Total duration of study drug exposure (Days) is defined as the sum of (study Day 1 to the last visit date plus 1).

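### SAP 6.2 defines infusion status 'completed' without reference to the 13 planned infusions, and no planned table counts who received all 13 or who stopped treatment for any reason

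*SAP*

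**What the plan says.** SAP 6.2 restates the regimen as an infusion at baseline, "then weekly for two weeks and then once every 2 weeks for the next 20 weeks (13 administrations) to subjects with SLE". Protocol 8.4 gives the same schedule.

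The section then plans a table of each subject's overall "infusion status (completed, interrupted or terminated) during the treatment period and the reason for interrupted or terminated will be summarized by treatment group". The first category is defined: "Overall infusion completed is defined as a subject without any infusion interruptions or terminations during the study". *Terminated* is not defined. *Interrupted* is used in the same section for an infusion that stopped and was restarted.

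On the denominator, SAP 6.2 says "The percentages will be calculated based on the number of subjects in each treatment group of the SAS", and SAP 3.1.3 says "The Safety Analysis Set (SAS) is defined as all subjects who received any treatment with either RSLV-132 or placebo". One infusion is enough to enter it.

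SAP 6.2 also summarizes:
- dosing duration, from first to last dose date plus 1;
- total number of infusions, obtained by summing infusion segments;
- total infusion hours and total volume infused;
- exposure, which runs to the last visit rather than the last dose.

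SAP 6.1 plans a row for "Number and percentage of subjects randomized and treated who completed the study" and rows for discontinuing the study, with reasons. It has no row for discontinuing study treatment. SAP 2.3.5 treats the two as different events. When a subject wishes to withdraw, "the site staff should confirm whether the subject is agreeable to continue the assessments without the investigational treatment", and the date and reason for stopping treatment go on the CRF.

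**The concern.** The primary objective concerns the effect of 13 infusions, and a secondary objective concerns the tolerability of 22 weeks of exposure. A reader of the study report will want to know how many subjects received the course, and will take a row headed *completed* as the answer. As defined, the row answers a different question: whether any infusion that was started was paused or cut short.

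The measure also moves the wrong way as a marker of delivery. Each further infusion can only remove *completed* status and can never confer it. Other things being equal, a subject who receives fewer doses is more likely to keep it. If early treatment stops differ between arms, the comparison of completed rates is distorted in favor of the arm with more stops.

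**Working it through.** **1. Planned number of infusions.** From the schedule in SAP 6.2 and Protocol 8.4: 1 at baseline + 2 weekly + 20/2 every two weeks = 13. Protocol 5.1 lists 13 dosing days (1, 8, 15, 29, 43, 57, 71, 85, 99, 113, 127, 141, 155). The plan's figure is reproduced.

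**2. The status rule applied as written.** *Terminated* is taken at the level of a single infusion. The section uses *interrupted* at that level, and SAP 2.3.5, 10.1.1 and 10.1.6 use *discontinuation* for stopping treatment.

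| Infusions received | Status under SAP 6.2 | Infusion count by segments | Dosing duration (days) | All 13 received? |
|---|---|---|---|---|
| 1, no pause | completed | 1 | 1 | no |
| 3, no pause | completed | 3 | 15 | no |
| 12, no pause | completed | 12 | 141 | no |
| 12, one pause | interrupted | 13 | 141 | no |
| 13, no pause | completed | 13 | 155 | yes |
| 13, one pause | interrupted | 14 | 155 | yes |

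Durations assume dosing on the scheduled days from Day 1 with no dose skipped: last day − 1 + 1. Every count from 1 to 12 without a pause gives *completed*.

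**3. Can another planned table supply the missing count?**
- *Total number of infusions*: a value of 13 can mean 13 clean infusions or 12 with one pause, so it does not identify who received the course.
- *Dosing duration*: shows early stopping but not skipped doses. A subject who missed Days 71 and 85 and was dosed on Day 155 shows 155 days with 13 − 2 = 11 infusions.
- *Exposure duration*: a subject last dosed on Day 15 who attends Day 215 shows 215 − 1 + 1 = 215 days.
- *SAP 6.1*: counts leaving the study, not leaving treatment.
- *SAP 10.1.1 and 10.1.6*: cover only stops caused by adverse events. They pool study drug discontinuation with study termination, and 10.1.6 also pools hospitalization.

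**4. How strongly the label favors fewer doses.** The documents give no interruption rate. Assume a probability p per infusion, independent across infusions. The chance of losing *completed* status over k infusions is 1 − (1 − p)^k.

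| Assumed p | k = 13 | k = 3 |
|---|---|---|
| 1% | 1 − 0.99^13 = 12% | 1 − 0.99^3 = 3% |
| 2% | 1 − 0.98^13 = 23% | 1 − 0.98^3 = 6% |
| 5% | 1 − 0.95^13 = 49% | 1 − 0.95^3 = 14% |

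These figures illustrate direction only. They do not estimate how many subjects will be misread.

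**5. Weight of one subject.** With about 50 subjects at 2:1, the active arm has about 50 × 2/3 = 33 and placebo about 17. One early stopper shown as *completed* adds 1/33 = 3.0 points in the active arm, or 1/17 = 5.9 points in placebo.

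**The case against.** The strongest reply is that the row describes how infusions ran, not whether the regimen was delivered. It is tabulated with the reason for interruption or termination, and calling a subject with a paused infusion *interrupted* is accurate for that purpose. This stands, and it is why the remedy is a new label plus a separate course-completion row rather than removal of the table.

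A second reply is that *terminated* is undefined and a programmer could read it to include permanent stopping, which would catch the early stopper. That is possible, though the SAP's own vocabulary points the other way. Even on that reading, a subject who skipped doses and resumed would be *completed*, and one with all 13 and a pause would not.

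A reader might infer three stronger conclusions that the documents do not support:

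- *That a null CLASI result could not be told apart from under-dosing.* Dosing duration and volume infused are summarized by arm, with minimum and maximum under SAP 5, and collected data are listed by subject. About 15 days of dosing against 155 would be visible.
- *That poor tolerability leading to stopping would be hidden.* SAP 10.1.1 and 10.1.6 tabulate adverse events leading to study drug discontinuation.
- *That an early stopper who stays for assessments will be shown as having completed the study.* SAP 6.1 does not define study completion, so this is likely but not certain.

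**Conclusion.** The point holds as a defect of definition and reporting. The *completed* category in SAP 6.2 does not measure receipt of the 13 infusions. The segment-based count cannot replace it, and no planned table gives the number who received all 13 or the number who stopped treatment for any reason.

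The early-stopper half rests on reading *terminated* per infusion. The other half, that 13 infusions with a pause and restart is not *completed*, holds on any reading.

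The consequence is limited. The status defines no analysis set and enters no efficacy or adverse-event analysis, and the trial plans no formal hypothesis testing. The total misstatement cannot be sized, because the documents give neither an interruption rate nor a treatment-discontinuation rate. What can be said is about 3 points per misread active subject and about 6 per placebo subject. It should be corrected because the label invites a wrong reading and the correction is cheap. It does not threaten the trial's conclusions.

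**What to change.** In SAP 6.2:
- rename the current category 'no infusion interrupted or terminated', and define *terminated*, saying whether it covers one infusion or the whole course;
- count infusions by distinct dosing visit, not by segment;
- report by arm the number and percentage of subjects who received all 13 planned infusions, counting an infusion that was paused, resumed and fully given as received;
- report interruptions separately.

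In SAP 6.1, add the number and percentage of subjects who discontinued study treatment, with reason, beside the existing rows on study discontinuation.

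The inputs exist: Protocol 8.4 has infusion start and stop times recorded, and SAP 2.3.5 has the date and reason for stopping treatment on the CRF. The cost is a wording change, one or two derived variables and a few table rows. The reported completion rate may be lower than under the current label. No clinical rule changes.

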6.3. Protocol Deviations

Deviations from the protocol will be documented on an ongoing basis on the protocol deviations eCRF throughout the study. Major protocol deviations will be determined prior to the database lock. The number and percentage of subjects within each major deviation category will be summarized by treatment group on the FAS. The percentages will be calculated based on the number of subjects in each treatment group of the FAS. The deviations collected on the eCRF will be listed.

Inclusion and exclusion criteria data will be listed for all subjects.

7. BASELINE DATA

7.1. Demographic and Baseline Characteristics

Demographic (age [years], gender, race, ethnicity, height [cm], weight [kg], BMI [kg/m²]) and baseline characteristics (CLASI activity score, Number and percentage subjects with oral corticosteroids dose [Overall mean, 0 mg/day, >0 and ≤7.5 mg/day, >7.5 mg/day]) will be summarized descriptively by treatment group on the FAS. For categorical parameters, the percentages will be calculated based on the number of subjects in each treatment group of the FAS.

7.2. Medical History

Number and percentage of subjects with medical history body systems will be summarized by treatment group for the FAS.

A subject with multiple occurrence of the same body system will be counted only once. Medical history body systems will be sorted alphabetically. The percentages will be calculated based on the number of subjects in each treatment group of the FAS.

8. PRIOR AND CONCOMITANT MEDICATIONS

8.1. Medications

Prior and concomitant medications will be coded using the World Health Organization (WHO) drug dictionary for anatomical therapeutic chemical classification (ATC) and preferred drug name. The most current version of dictionary available will be used for the coding. Number and percentage of subjects with each of the coded medications will be summarized by treatment group on the FAS. A subject who used multiple medications will be counted only once for each ATC and preferred drug name. ATC and preferred drug name within each ATC will be sorted alphabetically. The percentages will be calculated based on the number of subjects in each treatment group of the FAS. Prior and concomitant medications will be summarized separately. No inferential statistics will be performed.

Prior medications are defined as any medications that started and stopped prior to the date of first dose of study drug (RSLV-132 or Placebo). Concomitant medications are defined as any medications that started or were ongoing at or after the date of first dose of study drug (RSLV-132 or Placebo). Where a medication recorded with a partially or fully missing start/stop date or time, and it is unclear as to whether the medication is concomitant, it will be assumed that it is concomitant.

9. EFFICACY ANALYSES

Efficacy analyses include assessing improvement in disease activity using CLASI, SLEDAI-2K, BILAG-2004, PGA, and FACIT-Fatigue scores; tender or swollen joint count; oral steroids use; as well as evaluating the autoantibody and complement profiles.

Each assessment will be summarized descriptively by treatment group on the FAS for all study visits at which the data were collected. No statistical testing will be performed, unless otherwise specified.

All data will be listed.

9.1. Analysis of Primary Efficacy Endpoints

The primary efficacy endpoints are the improvements from Baseline (Day 1) to Day 85 and Baseline to Day 169 CLASI Activity scores.

CLASI Activity assessment will be performed for each subject at scheduled visits to determine the SLE disease activity for each subject at the visit. The assessment includes each anatomical location. The total score of the Activity subsection (defined as the sum of the scores from each anatomical location) will be used in the summary. The improvements from Baseline (Day 1) to Day 85 and from Baseline (Day 1) to Day 169 in the total activity score will be evaluated as part of the primary efficacy endpoints. Lower score represents less disease activity.

Summary of observed values: Observed values of total Activity score and the change and percent change from baseline at each scheduled visit will be summarized. In addition to the LOCF imputation described below, the primary endpoints (change from Baseline on observed values) will be analyzed using Mixed effect Model Repeat Measurement (MMRM) method. The MMRM model will include the fixed categorical effects of treatment, random effect visit, and treatment-by-visit interaction, as well as continuous fixed covariates of baseline score and baseline score-by-visit interaction. An unstructured covariance structure of random effect will be used for modeling the within-subject errors.

Summary of imputed values: LOCF imputed values and the change and percent change from Baseline (Day 1) in the CLASI Activity total score at Days 85 and 169 and at each scheduled visit will also be analyzed. The two-sample t-test will be used for the treatment group comparison on the change from Baseline.

Summary of non-censored values: Non-censored values and LOCF imputed non-censored values as well as the change and percent change from Baseline (Day 1) in the CLASI Activity total score at Days 85 and 169 and at each scheduled visit will also be analyzed. The two-sample t-test will be used for the treatment group comparison on the change from Baseline. The following values will be censored based on blinded review before database lock:

- a. Values obtained within 60 days of a steroid (systemic/oral/topical but not ophthalmic or inhaled) dose that is increased above baseline for more than one day
- b. Addition of other systemic agents for lupus (such as antimalarials, methotrexate, rituximab, dapsone)

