2.2. Endpoints**2.2.1. Efficacy Endpoints****2.2.1.1. Primary Efficacy Endpoints**

- Compare the treatment group difference in the mean improvement from Baseline to Day 85 in CLASI Activity scores of those in the efficacy analysis set receiving RSLV-132 and those receiving placebo.
- Compare the treatment group difference in the mean improvement from Baseline to Day 169 in CLASI Activity scores of those in the efficacy analysis set receiving RSLV-132 and those receiving placebo.

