9.2.1. SLEDAI-2K

Systemic Lupus Erythematosus Disease Activity Index SELENA Modification will be performed for each subject at scheduled visits to determine the SLE disease activity for each subject at the visit. The total score (defined as the sum of weights next to descriptors marked present) will be summarized. The improvements from Baseline (Day 1) to Day 85 and from Baseline (Day 1) to Day 169 in SLEDAI-2K total scores will be evaluated as part of the secondary efficacy endpoints. Lower score represents less disease activity.

Summary of observed values: Observed values of total score and the change from baseline at each scheduled visit will be summarized. In addition to the LOCF imputation described below, the change from Baseline on observed values will be analyzed using Mixed effect Model Repeat Measurement (MMRM) method as described in the SAP Section 9.1.

Summary of imputed values: Imputed values and the change from Baseline (Day 1) in the SLEDAI-2K total score at each scheduled visit will also be analyzed. The two-sample t-test will be used for the treatment group comparison on the change from Baseline. LOCF will be used to impute missing values on the FAS.

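### SAP 9.1 mis-specifies the MMRM: visit is labelled random and the status of treatment-by-visit is unclear, so one permitted reading does not estimate the Day 85 and Day 169 differences

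*SAP*

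**What the plan says.** The endpoints belong to two named visits. SAP 9.1 states: "The primary efficacy endpoints are the improvements from Baseline (Day 1) to Day 85 and Baseline to Day 169 CLASI Activity scores". SAP 2.2.1.1 words each as a between-arm comparison, for example: "Compare the treatment group difference in the mean improvement from Baseline to Day 169 in CLASI Activity scores".

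The MMRM is one of the planned analyses: "the primary endpoints (change from Baseline on observed values) will be analyzed using Mixed effect Model Repeat Measurement (MMRM) method". Its terms are given in one sentence, which begins "The MMRM model will include the fixed categorical effects of treatment, random effect visit, and treatment-by-visit interaction" and continues "as well as continuous fixed covariates of baseline score and baseline score-by-visit interaction". The covariance sentence is "An unstructured covariance structure of random effect will be used for modeling the within-subject errors".

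The section does not say which MMRM contrast will be reported. For the LOCF values, and again for the non-censored values, it plans a simpler comparison: "The two-sample t-test will be used for the treatment group comparison on the change from Baseline". Sections 9.2.1 (SLEDAI-2K), 9.2.3 (PGA), 9.2.4 (FACIT-Fatigue) and 9.2.5 (joint count) reuse the model by reference; in 9.2.1 the change is to be "analyzed using Mixed effect Model Repeat Measurement (MMRM) method as described in the SAP Section 9.1".

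**The concern.** A treatment difference at a named visit is normally a contrast among fixed treatment, visit and treatment-by-visit effects, with the covariance matrix describing the repeated errors within a subject. The text departs from that in three ways.

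- Visit is called random, yet the interaction of baseline with visit is called fixed. The two do not fit together.
- The unstructured matrix is assigned to a random effect and, in the same sentence, to the within-subject errors. These are different parts of a mixed model.
- Treatment-by-visit stands in a list that opens with fixed effects, but comes directly after the random visit term. Two competent programmers could code it differently, and no named contrast settles the matter.

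At stake is whether the MMRM estimates the primary endpoints or something else. The revision table in SAP Section 12 says the repeated-measures analysis was added because missing data bias it less than LOCF. It is also the only specified analysis of the primary endpoints that adjusts for baseline as a covariate. If the ambiguity is found only at programming, the model may be chosen with results in view.

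**Working it through.** The plan gives no figure to reproduce. The check asks which quantity each reading of the sentence estimates.

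**Inputs from the documents.** CLASI is scored after baseline on Days 29, 57, 85, 113, 141 and 169 (Protocol 12.5) and Days 99, 127 and 155 (Protocol 12.4), so nine visits. About 50 subjects are randomized 2:1, roughly 33 and 17.

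**Assumptions, not in the documents.** SD 6; correlation 0.6 between any two visits; true differences of -0.5, -1.0, -2.0, -2.3, -2.6, -3.0, -3.3, -3.6 and -4.0 in day order, so -2.0 at Day 85 and -4.0 at Day 169. Variance parameters were held fixed. Expected values use complete data. One simulated data set has 10 dropouts.

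**Step 1: what each reading estimates.**

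| Reading | Visit | Treatment-by-visit | Expected Day 85 | Expected Day 169 |
|---|---|---|---|---|
| A (standard) | fixed | fixed | -2.0 | -4.0 |
| B | random | fixed | -2.0 | -4.0 |
| C | random | random | -2.478 | -2.478 |

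Under B, treatment plus treatment-by-visit spans the same fixed-effect space as A: the design matrices have rank 27 for A, for B, and for both combined. A visit effect common to both arms cancels from the difference. In the simulated data, A and B gave identical results: -1.4156 (SE 1.7913) at Day 85 and -0.4565 (SE 1.8870) at Day 169, for random-visit variances of 0.5, 2 and 10. A random visit effect within subject, with an unstructured matrix, gave the same figures.

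Under C the fixed part holds a single treatment effect. Its expected value is the visit average: -22.3 / 9 = -2.478. Visit-specific values exist only as predictions shrunk towards that average. Their expected values at Days 85 and 169 are -2.347 and -2.901 for interaction variance 0.2, -2.155 and -3.520 for 1, and -2.043 and -3.875 for 4.

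**Step 2: size under reading C for CLASI.** Assume the effect grows linearly from zero at Day 1 to D at Day 169, so it is D × (day - 1)/168.

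- Sum of (day - 1): 28 + 56 + 84 + 98 + 112 + 126 + 140 + 154 + 168 = 966.
- Average: 966 / (9 × 168) = 0.639 D.
- Day 85 value: 84/168 = 0.50 D. Ratio 0.639/0.50 = 1.28, so Day 85 is overstated by 28%.
- Day 169 value: 1.00 D, so Day 169 is understated by 36%.

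If the effect instead starts only after Day 85 and rises linearly to D, the average is (14 + 28 + 42 + 56 + 70 + 84) / (9 × 84) = 294/756 = 0.389 D, against 0 at Day 85 and D at Day 169.

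**Step 3: the secondary endpoints, same linear assumption.** SLEDAI-2K, PGA and joint count have six post-baseline visits: (28 + 56 + 84 + 112 + 140 + 168) / (6 × 168) = 588/1008 = 0.58 D. FACIT-Fatigue has two: (0.50 + 1.00)/2 = 0.75 D.

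**Step 4: the covariance.** An unstructured 9 × 9 matrix has 9 × 10/2 = 45 parameters. Making visit random within subject and adding a separate residual gives 46, but with one score per subject per visit only 45 can be identified. For FACIT-Fatigue the counts are 4 and 3. The surplus parameter can trouble the fitting software; it does not change the contrasts when treatment-by-visit is fixed.

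**The case against.** A reader might infer that, because visit is called random, the model cannot produce the Day 85 and Day 169 differences. The documents do not support that. Only visit carries the random label. The list opens with fixed effects and ends with treatment-by-visit, so the most literal reading is B, which gives exactly the standard contrasts. The explicitly fixed baseline-by-visit term also points to visit-specific fixed modelling. A reader might likewise infer that a within-subject random visit term breaks the analysis; it adds a redundant parameter but leaves the estimates alone. Nor does the text ask for an extra residual on top of the unstructured matrix.

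The defence goes further. The MMRM is additional to the LOCF analysis, whose t-tests compare the arms at both days however the MMRM is coded. SAP 2.3.7, 3.2.3 and 5 plan no formal hypothesis testing and treat p-values as descriptive, so no decision rule turns on this model.

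All of this stands, and it limits the size of the problem. It does not make the sentence clear. An interaction with a random factor is conventionally random too, and the text states afresh that the baseline covariates are fixed, which suggests that the preceding terms need not be. Reading C therefore remains open to a programmer acting in good faith. Relying on LOCF would also give up the reason recorded for adding the MMRM.

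**Conclusion.** The concern holds as a specification error with an ambiguous consequence. SAP 9.1 labels visit wrongly, confuses the random-effect matrix with the within-subject error matrix, and leaves the status of treatment-by-visit unclear. With a fixed interaction, the primary contrasts are unaffected. With a random interaction, the fixed part of the model yields one visit-averaged contrast for both days and the primary endpoints are not estimated.

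The figures of 0.64 D and 0.39 D apply only to the random-interaction reading, to the assumed growth shapes, and to equal weighting of the nine visits. With missing data or another covariance pattern the weights can change, but the contrast is still one number for both days. That estimability result does not depend on the assumed SD, correlation or effects.

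This should be corrected before database lock, but it ranks below a must-fix defect: the LOCF t-tests still give both comparisons, and p-values are descriptive.

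**What to change.** Rewrite the model sentences in SAP 9.1 to say three things.

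1. Treatment, categorical visit, treatment-by-visit, baseline score and baseline-by-visit are all fixed effects.
2. The unstructured covariance applies to the repeated within-subject errors across visits, with no random visit term.
3. The reported MMRM results are the adjusted mean differences between arms, with 95% confidence intervals, at Day 85 and Day 169.

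Sections 9.2.1 and 9.2.3 to 9.2.5 inherit the correction through their cross-references. The cost is a few sentences before database lock, with no change to data, sample size or conduct.

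Kenward-Roger degrees of freedom and a pre-set order of simpler covariance structures, in case the 45-parameter matrix does not converge in about 50 subjects, would be good practice. They are optional and not part of the error.
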